3.3.2 Exclusion Criteria

Subjects must meet none of the criteria below:

1. Subject has a history of anaphylactic reactions to blood or blood products that may interfere with participation in the study in the opinion of the investigator.
2. Subject has uncontrolled hypertension.
3. Subject has clinical or laboratory evidence of an intercurrent infection as evidenced by symptoms including fever, tachycardia, or other systemic signs and symptoms. (Note: Subjects with an intercurrent infection cannot participate; however, once the infection has resolved as judged by the investigator, they can be re-screened if enrollment is still open.)
4. Subject is pregnant and/or lactating.
5. Subject has a malignancy, except for basal or squamous cell skin cancer, within 3 years before screening.
6. Subject is a previous organ transplant recipient.
7. Subject is in receipt of exogenous plasminogen (ocular or IV), such as laboratory grade plasminogen, fresh frozen plasma, or Prometic Plasminogen (Human) within 2 weeks of the screening visit.
8. Subject has a psychiatric disorder, other mental disorder, or any other medical disorder that impairs the subject's ability to provide informed consent or to comply with the requirements of the study protocol.
9. Subject has evidence of renal dysfunction defined as of $> 2 \times$ the upper limit of normal (ULN) in serum creatinine.
10. Subject has evidence of hepatic dysfunction defined as $> 3 \times$ ULN in alanine aminotransferase (ALT), aspartate aminotransferase (AST), or alkaline phosphatase (ALP).

11. Subject has participated in another IRB-approved interventional clinical trial of a drug, biologic, or device within 30 days before the first dose of the IMP.
12. Subject has a chronic or acute clinically significant inter-current illness (e.g., cardiac, hepatic, renal, endocrine, neurologic, hematologic, neoplastic, immunological, and skeletal) that the investigator determines could interfere with the assessments in this study.

3.4 Measures to Minimize or Avoid Bias

3.4.1 Randomization

Subjects will not be randomized.

3.4.2 Blinding

This study will not be blinded.

3.5 Study Procedures

The schedule of events is provided in Table 2.

Table 2. Schedule of Events by Visit

	Screening (≤ 21 days)	Segment 1 ^a		Segment 2 ¹							Segment 3 ¹	End of Study Visit for Subjects at US Site Only ^o	Safety Follow-up	
		Day - 4	Day - 3, Day - 2, Day - 1	Week 1 Day 0	Week 2 ^b	Week 4	Week 6 ^b	Week 8	Week 10 ^b	Week 12 ^c	Every 12 Weeks	30 days post final dose		
Informed consent/ assent	X													
Eligibility review	X													
Demographics	X													
Medical history	X	X ⁱ		X ^j										
Disease history & treatment	X	X ⁱ		X ^j										
Medication history	X	X ⁱ		X ^j										
Weight	X	X ⁱ		X ^j						X	X	X	X	
Physical examination	X	X ⁱ		X ^j						X	X	X	X	
Urine pregnancy test ^d	X	X ⁱ		X ^j		X		X		X	X			
Genetic test ^e	X	X ⁱ		X ^j										
Hematology	X	X ⁱ		X ^j		X		X		X	X	X	X	X
Biochemistry	X	X ⁱ		X ^j		X		X		X	X	X	X	X
Urinalysis	X	X ⁱ		X ^j		X		X		X	X	X	X	X
Fibrinolysis & coagulation panels	X	X ⁱ		X ^j		X		X		X	X	X	X	X
Virology	X	X ⁱ		X ^j						X	X	X	X	X
Retention virology sample		X ⁱ		X ^j										
Anti-plasminogen antibody		X ⁱ		X ^j		X		X		X	X	X	X	X
Plasminogen activity and antigen, D-dimer: trough levels	X			X	X	X	X	X	X	X	X			X
Plasminogen activity and antigen, D-dimer: spot levels													X	

	Screening (≤ 21 days)	Segment 1 ^a		Segment 2 ¹							Segment 3 ¹	End of Study Visit for Subjects at US Site Only ^o	Safety Follow-up	
		Day - 4	Day - 3, Day - 2, Day - 1	Week 1 Day 0	Week 2 ^b	Week 4	Week 6 ^b	Week 8	Week 10 ^b	Week 12 ^c	Every 12 Weeks		30 days post final dose	
Plasminogen activity and antigen, D-dimer: PK profile ^f		X	X	X ^k							X			
Clinical assessments ^g		X ^j		X ^j		X		X		X	X	X	X	X
Clinical Global Impression		X ^j		X ^j		X		X		X	X ⁿ			
Quality of life assessment		X ^j		X ^j		X		X		X	X ⁿ			
Chest X-ray		X ^{j,m}		X ^{j,m}						X ^m				
Vital signs ^h	X	X		X	X	X	X	X	X	X	X			
IMP infusion ⁱ		X		X	X	X	X	X	X	X	X			
Concomitant medications		X	X	X		X		X		X	X	X	X	X
AE assessment		X	X	X		X		X		X	X	X	X	X
Subject diary				X		X		X		X	X	X	X	X

AE = adverse event; IMP = investigational medicinal product; PK = pharmacokinetic.

- a. For subjects who do not have PK profile for 6 mg/kg Plasminogen on file only. Those who have PK profile on file (e.g., they participated in the previous Phase 1, Cohort 2 study) do not need to go through Segment 1 and can directly enter Segment 2.
- b. Weeks 2, 6 and 10 visits may be performed at subject's home by a home health nurse or at an ancillary site in lieu of the study site.
- c. The Week 12 visit is the end of treatment in Segment 2. Subjects are asked to Segment 3 based on Investigator's and Sponsor's decision. Subjects who discontinue the study during Segment 2 are required to undergo these assessments as well, except IMP infusion.
- d. Women with child-bearing potential only.
- e. Genetic test for hypoplasminogenemia is optional. Subjects who already have known test results or who do not wish to participate can omit the test.
- f. See Section 3.5.2.6 for PK sampling time points.
- g. The types and timing of clinical assessments depend on each subject's disease presentation and include but are not limited to: 1) measurement of visible lesions using photographs, 2) functionality tests (e.g., spirometry), 3) imaging of non-visible lesions (e.g., ureteral, oropharyngeal and bronchial) based on the investigator's discretion. See Section 3.5.2.13 for details.
- h. Vital signs are taken within 15 minutes before and 15 minutes after each infusion that takes place at the study site and when a home health nurse is present during a visit.
 - i. At each study visit, the IMP is infused by study staff on site. Between study visits, the IMP is infused at the site or an ancillary site, or at home by a home health nurse or self-administered by the subject or a caregiver. See Section 3.2 for details. Subjects' infusions window for both Segment 2 and Segment 3 is +/- 1 day.
- j. For subjects who participate in Segment 1, these baseline assessments are performed on Day -4 only. For subjects who do not participate in Segment 1 and are directly entering Segment 2, these baseline assessments

are performed on Day 0 only. Any of these assessments that have already been performed at Screening within the past 7 days may be omitted.

- k. A pre-infusion sample for PK profile is required for subjects in Segment 1 only (i.e., the 96-hour time point). Subjects directly entering Segment 2 do not require PK profile.
- l. Visit windows for Segment 2 are +/- 1 day and for Segment 3 are +/- 7 days. Visit windows for the Safety Follow-up, 30 days post final dose, are +/- 3 days.
- m. A chest X-ray will be performed at baseline and Week 12 at the investigator's discretion.
- n. The Clinical Global Impression and Quality of life assessment will be performed at the Week 48 Visit only in Segment 3.
- o. Subjects who decide to enter Treatment Protocol 2002C018G will return to the study site and complete the End of Study visit and sign an informed consent/assent for that study and stop participation in the current study. Subjects who decide not to enter Treatment Protocol 2002C018G will stop IMP and return to the study site for the Safety Follow-up visit 30 days after the final IMP dose.

3.5.1 Procedures by Visit

3.5.1.1 Screening

- Informed consent/assent
- Eligibility review
- Demographics
- Medical history
- Disease history and past and current treatment
- Medications taken in the past year
- Weight
- Vital signs (temperature, respiratory rate, BP, and heart rate)
- Physical examination
- Blood sample for genetic test (if not on file)
- Blood and urine samples for clinical laboratory tests (hematology, biochemistry, urinalysis, fibrinolysis panel, coagulation panel) (Appendix 15.2)
- Blood samples for plasminogen activity, antigen, D-dimer
- Blood sample for virology serology (results are not required to begin dosing)

3.5.1.2 Baseline Assessments (Either Segment 1, Day -4 or Segment 2, Day 0)

The following baseline assessments will occur before the first dose of IMP. For subjects participating in Segment 1, the baseline assessments will occur on Day -4. For subjects directly entering Segment 2, the assessments will occur on Day 0.

Any of the assessments that have been conducted at Screening within 1 week before Baseline may be omitted at the Investigator's discretion, and the results from Screening may be used as Baseline values.

- Weight
- Vital signs
- Physical examination
- Changes in medical history, disease history and current medications
- Blood and urine samples for clinical laboratory tests (hematology, biochemistry, urinalysis, fibrinolysis panel, coagulation panel)
- Blood samples for plasminogen activity, antigen, D-dimer
- Retention blood samples for virology (PCR)
- A blood sample for virology serology
- A blood sample for anti-plasminogen antibody
- Clinical assessments (Section 3.5.2.13)
 - Measurements and photographs of visible lesions
 - Imaging of non-visible lesions
 - Functionality testing
- Clinical Global Impression
- Quality of life assessment
- Chest X-ray, at the investigator's discretion
- Urine pregnancy test (women of childbearing potential)

3.5.1.3 **Segment 1, Week 0, Day -4 (Participants Only)**

Segment 1 is required only for subjects without a prior PK profile on file for 6 mg/kg Plasminogen (Section 3.1). Baseline assessments (Section 3.5.1.2) should be completed before the IMP administration.

- Vital signs (before and 15 minutes after infusion)
- IMP infusion
- Blood samples (post-dose) for PK profile: plasminogen activity, antigen, and D-dimer (Section 3.5.2.6)
- Concomitant medications
- AE assessment

3.5.1.4 **Segment 1, Week 0, Day -3, Day -2, and Day -1 (Participants Only)**

- Blood samples for PK profile: plasminogen activity, antigen, and D-dimer (Section 3.5.2.6)
- Concomitant medications
- AE assessment

3.5.1.5 **Segment 2, Week 1, Day 0**

For subjects with prior PK profile on file and directly entering Segment 2, the Baseline assessments (Section 3.5.1.2) will be completed before the IMP administration, followed by the procedures below.

Any of the assessments that have been conducted at Screening within 2 weeks before this visit may be omitted, and the results from Screening may be used as Baseline values.

- Vital signs (before and 15 minutes after infusion)
- IMP infusion
- Concomitant medications
- AE assessment
- Provision of subject diary and instructions

For subjects entering Segment 2 after completing Segment 1, Baseline assessments are not needed. Instead, the following procedures will be conducted:

- Prior to IMP infusion, blood samples for trough plasminogen activity, antigen, and D-dimer (i.e., the 72-hour sample after first dose)
- Vital signs (before and 15 minutes after infusion)
- IMP infusion
- Concomitant medications
- AE assessment
- Provision of subject diary and instructions

3.5.1.6 **Segment 2, Week 2, Week 6, Week 10**

These visits will occur either at the study site or ancillary site, or at the subject's home by a home health nurse (US subjects only).

- Prior to IMP infusion, blood samples for trough plasminogen activity, antigen, and D-dimer
- Vital signs (before and 15 minutes after infusion)

- IMP infusion

3.5.1.7 **Segment 2, Weeks 4 and 8**

- Clinical assessments (Section 3.5.2.13)
 - Measurements and photographs of visible lesions
 - Imaging of non-visible lesions
 - Functionality testing
- Clinical Global Impression
- Quality of life assessment
- Urine pregnancy test (women of childbearing potential)
- Prior to IMP infusion, blood and urine samples for clinical laboratory tests (hematology, biochemistry, urinalysis, fibrinolysis panel, coagulation panel)
- Prior to IMP infusion, a blood sample for anti-plasminogen antibody
- Prior to IMP infusion, blood samples for trough plasminogen activity, antigen, and D-dimer
- Vital signs (before and 15 minutes after infusion)
- IMP infusion
- Concomitant medications
- AE assessment
- Review and provision of subject diary

3.5.1.8 **Segment 2, Week 12 or Discontinuation**

The following assessments will be conducted at the study site at Week 12 or at the final visit if a subject discontinues treatment:

- Weight
- Physical examination
- Urine pregnancy test (women of childbearing potential)
- Clinical assessments (Section 3.5.2.13)
 - Measurements and photographs of visible lesions
 - Imaging of non-visible lesions
 - Functionality testing
- Clinical Global Impression
- Quality of life assessment

- Chest X-ray, at the investigator's discretion
- Prior to IMP infusion, blood and urine samples for clinical laboratory tests (hematology, biochemistry, urinalysis, fibrinolysis panel, coagulation panel)
- Prior to IMP infusion, blood samples for virology (serology and PCR) testing
- Prior to IMP infusion, a blood sample for anti-plasminogen antibody
- Prior to IMP infusion, blood samples for trough plasminogen activity, antigen, and D-dimer
- Vital signs (before and 15 minutes after infusion)
- IMP infusion (not administered if subject is discontinuing treatment)
- Blood samples for PK profile: plasminogen activity, antigen, and D-dimer (Section 3.5.2.6, not conducted if subject is discontinuing treatment)
- Concomitant medications
- AE assessments
- Review and collection of subject diary

3.5.1.9 Segment 3

The following assessments will be conducted at the study site every 12 weeks for 36 weeks in Norway or until the IMP licensing or study termination by the sponsor in the United States. During Segment 3, subjects will continue to receive the IMP at the same dosage and interval as Segment 2, with the possibility of modification based on discussion between the investigator and the sponsor. Subjects or their caregivers may administer the IMP at home if properly trained.

- Weight
- Vital signs
- Physical examination
- Urine pregnancy test (women of childbearing potential)
- Clinical assessments (Section 3.5.2.13), if indicated
 - Measurements and photographs of visible lesions
 - Imaging of non-visible lesions
 - Functionality testing
- Prior to IMP infusion, blood and urine samples for clinical laboratory tests (hematology, biochemistry, urinalysis, fibrinolysis panel, coagulation panel)
- Prior to IMP infusion, blood samples for virology (serology and PCR) testing
- Prior to IMP infusion, blood samples for anti-plasminogen antibody
- Prior to IMP infusion, blood samples for trough plasminogen activity, antigen, and D-dimer

- Vital signs (before and 15 minutes after infusion)
- IMP infusion
- Concomitant medications
- AE assessments
- Provision and review of subject's diary
- Clinical Global Impression (performed at the Week 48 Visit only)
- Quality of life assessment (performed at the Week 48 Visit only)

3.5.1.10 End of Study Visit for Subjects at the US Site Only

The following assessments will be conducted for subjects at the US site who decide to enter Treatment Protocol 2002C018G:

- Weight
- Physical examination
- Blood and urine samples for clinical laboratory tests (hematology, biochemistry, urinalysis, fibrinolysis panel, coagulation panel)
- Blood sample for virology (serology and PCR) testing
- Blood sample for anti-plasminogen antibody
- Blood samples for spot plasminogen activity, antigen, and D-dimer
- Concomitant medications
- AE assessment
- Review and collection of subject diary

Safety Follow-up Visit The following assessments will be conducted 30 days after the last dose of IMP has been administered

- Weight
- Physical examination
- Blood and urine samples for clinical laboratory tests (hematology, biochemistry, urinalysis, fibrinolysis panel, coagulation panel)
- Blood sample for virology (serology and PCR) testing
- Blood samples for trough plasminogen activity, antigen, and D-dimer
- Blood sample for anti-plasminogen antibody

- Concomitant medications
- AE assessment
- Review and collection of subject diary

3.5.2 Description of Assessments

3.5.2.1 Informed Consent/Assent

Informed consent is a process that includes the signing of the Informed Consent Form (ICF) for all subjects. Assent will be required from subjects younger than 18 years with consent from their legally authorized representative according to state law. Patients should be approached according to site policies regarding confidentiality. Potential subjects should be informed about the study according to the requirements of International Conference of Harmonisation (ICH) Good Clinical Practice (GCP). The informed consent process involves the investigator, and the subject should have the opportunity to discuss all aspects of the study, ask questions, consider the ICF/assent and statements, and provide an informed decision regarding any potential risks and any potential benefits. Both ICFs and assent, if applicable, must be signed prior to any study procedures being conducted. The informed consent/assent process continues throughout a subject's participation in the study. Subjects have the right to withdraw from the study for any reason and at any time. A separate genetic testing consent will be required.

3.5.2.2 Demographics

Demographic information will be collected, including the subject's date of birth, race, ethnicity, and sex.

3.5.2.3 Medical History and Disease History and Symptoms

A complete medical and surgical history will be obtained. If the subject is biologically or surgically unable to reproduce offspring, the reason for sterility should be recorded as a diagnosis (males and females).

At least 1 year of documented general history are recorded.

As part of the medical history assessment the investigator or designee will obtain a complete and detailed documented history regarding the progression of hypoplasminogenemia within at least 1 year before screening, including any surgeries performed, other treatments, and all symptoms of the disease (e.g., ligneous conjunctivitis). In addition, the investigator will interview the subject and record any self-reported lifetime history and treatment of the disease, including the date when the disease was originally diagnosed.

3.5.2.4 **Prior Medications and Treatments**

Documented prior and current medications within at least 1 year before screening will be recorded, including non-prescription, prescription, herbal/natural, blood products, and birth control for males and females who are able to reproduce at the time of screening. Records will include dates of use, indications, routes, doses, and schedules as appropriate. Corresponding diagnoses will also be recorded in the medical history with dates of diagnoses.

3.5.2.5 **Plasminogen Genetic Test**

Optional plasminogen genetic testing will be conducted at screening for those subjects who provide written informed consent form for genetic testing. A blood sample will be obtained, centrifuged, transferred to, and frozen in a cryovial and stored at -20°C. Genetic testing will be conducted by a Central Laboratory using a validated method developed by Machaon. Please see Laboratory Manual for more details on processing and shipping of blood samples. The genetic test is not necessary if the subject has undergone genetic testing in the past and the test result is available.

3.5.2.6 **PK Analyses for Plasminogen Activity and Antigen Levels**

Blood samples will be drawn and analyzed for plasminogen activity and plasminogen antigen levels at a Central Laboratory using validated assays. Plasminogen activity is assessed with a chromogenic assay developed and validated at a central specialty laboratory. Plasminogen antigen levels are determined by ELISA (Cell Sciences) and validated at a central specialty laboratory. For each sample taken for Plasminogen activity and antigen testing in Segments 1, 2, and 3 a backup sample will also be taken and stored at the Central Laboratory facility in case of repeat testing requirements. No backup sample is needed at the End of Study visit for subjects who decide to enter the treatment protocol.

Segment 1

Blood samples are drawn on Day -4 before the IMP infusion to establish baseline levels for plasminogen activity, antigen, and D-dimer and at the following time points after the end of the infusion: between 5 and 15 minutes, 6 hours (± 30 minutes), 24 hours (± 2 hours, Day -3), 48 hours (± 2 hours, Day -2), 72 hours (± 2 hours, Day -1), and 96 hours (± 2 hours, Day 0). An individual PK profile will be developed based on these time points.

Subjects who have had individual PK profile for 6 mg/kg Plasminogen with the sponsor, due to participation in the prior Phase 1 study, do not participate in Segment 1.

Segment 2

For subjects who do not undergo Segment 1, blood samples are drawn to measure plasminogen activity and antigen levels on Week 1, Day 0, before the first dose of the IMP is given, to establish the baseline levels.

For all subjects, blood samples will be drawn every 2 weeks before IMP infusion to measure trough levels through the final dose.

A full PK profile will also be done for all subjects at the end of Segment 2 (Week 12 visit) to evaluate the stability of individual PK profile after 12 weeks of IMP administration. As plasminogen is a consumable clotting factor, if significant lesion burden is present at the start of the study or if neutralizing antibody develops, a subject's PK profile may be altered by the end of the 12-week treatment period. At the Week 12 visit, blood samples are drawn before the IMP infusion and at the following time points after the end of the infusion: between 5 and 15 minutes, 6 hours (± 30 minutes), 24 hours (± 2 hours), 48 hours (± 2 hours), 72 hours (± 2 hours), and 96 hours (± 2 hours). The PK profile will be developed for each subject and compared with his or her prior PK profile(s).

Furthermore, additional PK analyses may be performed at other time points during Segment 2 as needed, such as when a subject's trough level or antibody test suggests the appearance of neutralizing antibody against the IMP or when the dosing frequency has changed.

Segment 3

Blood samples will be drawn at each study visit every 3 months before IMP infusion to measure trough levels. Plasminogen activity and antigen, D-dimer spot levels will be measured at the End of Study visit for subjects who decide to enter Treatment Protocol 2002C018G.

PK Sample Handling:

Blood samples will be obtained, centrifuged, and resulting plasma will be transferred to, and frozen in a cryovial and stored at -20°C . All samples will be shipped frozen to a Central Laboratory for analysis. Details on processing and shipping of blood samples are provided in the Laboratory Manual.

3.5.2.7 Clinical Laboratory Tests

Specimens for laboratory analysis will be obtained to ascertain if the subject meets eligibility criteria and to assess for abnormal changes and possible AEs during the study. The laboratory tests include hematology, serum chemistry, urinalysis, fibrinolysis and coagulation panels, and urine pregnancy test (as applicable). See Appendix 15.2 for a list of specific tests to be conducted.

Abnormal laboratory results will be reviewed by the investigator. Clinically significant abnormalities or changes from baseline will be reported as AEs, according to the investigator's judgment. However, changes that are associated with clinical improvement (for example, blood clot discharged in urine, increases in D-dimer) are not reported as AEs.

Details of sample collection and shipping will be outlined in the Laboratory Manual provided by the Central Laboratory.

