In the current study, an interim analysis was performed after the first 10 subjects completed 12 weeks of treatment with a data cutoff at 30 November 2016. All 10 of these subjects achieved target PK trough levels demonstrating the ability of Prometic's Plasminogen (Human) to serve as effective replacement therapy. Preliminary efficacy evaluation at 12 weeks revealed that 13 of 14 visible lesions had resolved, and the remaining lesion had improved from 15 × 5 mm at baseline to too small to be measured at 12 weeks. There were no recurrences and no new lesions during this period of observation. There were no deaths, serious adverse events (SAEs), or AEs resulting in discontinuation of study drug. The most frequent AEs were headache and nasopharyngitis. Nausea, diarrhea, rhinorrhea, sinusitis, epistaxis, back pain, pain in extremity, and hematuria were also frequent in adult subjects, and upper abdominal pain and cough were frequent AEs in pediatric subjects. A US Biologics Licensing Application was submitted based on these interim data; this application is under review. As of 14Dec2017 study enrollment is complete and all 15 enrolled subjects received at least 48 weeks of treatment. Three subjects in Norway completed the study as planned, with the remaining 12 subjects in the US continuing treatment until product licensing or study termination by the Sponsor. However, due to the delay in product approval, subjects at the US site will be allowed to enroll in Treatment Protocol 2002C018G and continue ongoing IMP treatment without any break in treatment. If subjects decide to enter Treatment Protocol 2002C018G, then they will return to the study site and complete the End of Study visit and sign an informed consent/assent for that study and stop participation in the current study. If subjects decide to not enter Treatment Protocol 2002C018G,

then they will stop IMP and return to the study site for a Safety Follow-up visit 30 days after the final IMP dose.

Subject dosing has been revised throughout the protocol from 6.0 mg/kg to 6.6 mg/kg of plasminogen to reflect the true concentration and dosing as agreed with FDA during the 05Oct2016 Pre-BLA Meeting (CRMTS# 10393).

Details of these studies can be found in the Investigator's Brochure (IB).

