3.6.2 Stopping Rules

Any subject who experiences any of the following occurrences will suspend the IMP treatment until further assessments:

- Anaphylactic response to study drug administration
- A significant AE that, in the investigator's opinion, necessitates suspension of treatment
- Confirmed presence of neutralizing antibodies (in at least 2 measurements) in association with diminished plasminogen activity that obviates the potential benefit of plasminogen replacement therapy.
- Thrombotic or uncontrolled bleeding event requiring hospitalization

The SMC will review safety data on an ongoing basis and will determine if a subject should stop treatment, or if there are unforeseen events (e.g., thromboembolic event) that would warrant halting or stopping the study. Such events will be discussed with FDA before enrolling further subjects.

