5.1 Definitions

5.1.1 Adverse Event

An AE is any untoward medical occurrence (whether or not considered to have a causal relationship to IMP) in a study subject administered an IMP. Therefore, an AE can be any unfavorable and unintended sign (including clinically significant laboratory finding), symptom, or disease temporally associated with the use of an IMP, whether or not related to the IMP.

However, signs and observations that are associated with clinical improvement (such as discharge of blood clots in urine), as judged by the investigator, will not be reported as AEs.

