6.3.3 Efficacy Analysis

The primary endpoint is:

Overall Clinical Success in number and size of lesions or change in organ functionality at 48 weeks

The secondary efficacy endpoints are:

- Overall Clinical Success in number and size of lesions or change in organ functionality at 12 weeks
- CGI scores at 12 and 48 weeks
- Quality of life scores at 12 and 48 weeks

Overall clinical success is defined as 50% of subjects with visible or other measureable lesions achieving at least a 50% improvement in lesion number/size or functionality impact from baseline. Visible lesions are defined as lesions which can be imaged and analyzed with digital photography. Other measureable lesions are defined as lesions whose dimensions can be assessed by medical imaging studies (e.g. computed tomography, magnetic resonance imaging, ultrasound, etc) or functional assessments (e.g. spirometry, audiogram, oximetry, etc).

Clinical success will be further described as a graded evaluation of potential clinical responses; 1) Excellent response: $\geq 75\%$ decrease; 2) Good response: $\geq 50\%$ and $< 75\%$ reduction; 3) Moderate response: $\geq 25\%$ to $< 50\%$ reduction; 4) Minimal response: $< 25\%$ reduction; 5) No response: an increase or no reduction in the size of the lesion. Clinical responses will be determined by the principal investigator for the assessment of clinical success.

All efficacy results will be presented descriptively by individual subjects, including summarized hypoplasminogenemia symptoms over time recorded in subject diaries. The small sample size and high variability of disease presentation do not allow formal statistical analyses.

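### Urinary clots and D-dimer rises regarded as clinical improvement are kept out of AE reporting with no criterion and no second review, so they are missing from the TEAE tables

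*Protocol*

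**What the plan says.** Section 3.5.2.7 sets a general rule for laboratory results: "Clinically significant abnormalities or changes from baseline will be reported as AEs, according to the investigator's judgment". It then makes an exception: "changes that are associated with clinical improvement (for example, blood clot discharged in urine, increases in D-dimer) are not reported as AEs". Section 5.1.1 makes a parallel exception inside the AE definition. Signs and observations that go with improvement, with passed urinary clots as the only example, "as judged by the investigator, will not be reported as AEs".

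The setting matters. Section 3.4.2 states "This study will not be blinded", there is no comparator, and Section 6.3.3 adds "Clinical responses will be determined by the principal investigator for the assessment of clinical success". Safety and tolerability are a secondary objective (Section 2.2). Section 6.3.4 plans descriptive summaries of TEAEs and SAEs, and separate summary and shift tables for laboratory tests.

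**The concern.** A clot in the urine or a rise in D-dimer may mean that a fibrin lesion is dissolving, which is the intended effect, or it may be an unwanted event. The protocol has this question settled before anything is recorded as an AE, and the answer decides whether a record exists. The usual order is to record the observation and then interpret it. The protocol has the tools for that: Section 5.1.1 defines an AE without regard to causal relationship, and Section 5.1.5 supplies a four-point causality scale.

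The exclusion works in one direction, since it can only lower AE counts. Under Section 5.1.1 it rests on the judgement of an unblinded investigator, and the principal investigator also judges efficacy. The same reading of an event can thus support a response and remove an AE. At stake is whether the TEAE summary of a small pivotal study can be taken as complete for these observations.

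**Working it through.** The protocol attaches no figure to this rule, so the check compares sections.

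**1. Criterion and decision-maker.** Neither Section 3.5.2.7 nor Section 5.1.1 says what makes a change associated with improvement. Section 5.1.1 names the investigator as judge but does not mention D-dimer. Section 3.5.2.7 names D-dimer, but its exclusion sentence does not say who decides. Neither section provides for a second review.

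**2. What an excluded observation misses.** Each later step starts from a recorded AE:
- grading of severity, seriousness and relatedness (Section 5.2);
- evaluation of every AE as a potential SAE (Section 5.3);
- the medical monitor's causality review before database lock (Section 5.1.5);
- the TEAE summaries (Section 6.3.4).

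**3. What record remains.**

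| | D-dimer rise | Clot passed in urine |
|---|---|---|
| Scheduled measurement | Yes: fibrinolysis panel, and with each trough or PK sample (Appendix 15.2) | Indirect: urinalysis covers protein, albumin and RBC (Appendix 15.2), at Weeks 4, 8 and 12 and then every 12 weeks (Table 2) |
| Planned safety table | Fibrinolysis/coagulation summary and shift tables (Section 6.3.4) | None counts clots; urinalysis results only |
| Committee review | Laboratory data (Section 3.7) | Urinalysis values only, unless the clot is also reported as an AE |
| Other record | – | Diary symptoms (Section 3.5.2.12), summarized under efficacy (Section 6.3.3) |

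A D-dimer rise is lost as an AE but not as a value. A passed clot may survive only as a diary entry, presented with efficacy and not with safety.

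**4. Status of D-dimer.** Section 6.3.2 treats D-dimer as a potential pharmacodynamic marker whose relationship to response is still to be explored. Section 3.5.2.7 already gives a rise as an example of improvement. The recording rule assumes an answer to a question that the study leaves open.

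**5. Scale only.** With the 15 treated subjects of Section 1.3, one subject with an unrecorded event changes an incidence by 1/15 = 6.7 percentage points. If 0 of 15 are recorded, the exact two-sided 95% upper limit is 1 − 0.025^(1/15) = 21.8%. These figures hold for any AE in a study of this size. They show that single events matter; they do not estimate a bias from this rule.

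**The case against.** The strongest defence is that the rule is narrow and fits the AE definition. An AE is an unfavourable and unintended sign, and clearing fibrin lesions is what plasminogen replacement is meant to do. Investigator judgement already governs all laboratory AEs under Section 3.5.2.7. D-dimer is measured often, tabulated whatever its AE status, and seen by a committee with an independent Medical Monitor, biweekly in Segments 1 and 2 and periodically in Segment 3. Diaries and urinalysis give a partial trace of urinary events. Case report form and table design are often settled outside the protocol, and enrollment is already complete.

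Much of this stands, and it rules out several stronger readings that a reader might infer:
- **That bleeding or thrombotic signals disappear from the safety tables.** The exclusion names passed clots and D-dimer rises, not blood in urine, and not bleeding or thrombosis in general. Section 1.3 reports that "pain in extremity, and hematuria were also frequent in adult subjects" among the interim AEs, so urinary bleeding was being recorded. "Thrombotic or uncontrolled bleeding event requiring hospitalization" remains a separate suspension criterion in Section 3.6.2, and an untoward event that meets an SAE criterion in Section 5.1.3 is still an SAE.
- **That no other record exists, or that nobody could check the judgement later.** This is wrong for D-dimer and only partly true for clots.

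The defence does not supply a criterion or a second look at the decision to exclude. Nor is this a detail that can be left to an analysis plan: the protocol itself fixes the rule, and an analysis plan cannot tabulate as TEAEs what was never reported as AEs. Hematuria reported as an AE and a urinary clot excluded as improvement may overlap, and the protocol offers no way to separate them.

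**Conclusion.** The point holds as a defect in AE recording. Clots passed in urine and D-dimer rises regarded as improvement are excluded from AE reporting without a criterion or a second review. They therefore miss the TEAE tables and the severity, seriousness and causality steps. The consequence is limited for D-dimer and larger for urinary clots.

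The direction is known: AE counts can only fall. The size is not. The protocol shows no excluded event, and the 6.7-point and 21.8% figures must not be read as the bias. The conclusion rests on the protocol as written and assumes that no case report form or study manual, neither of which is at hand, already captures the excluded observations separately. The change is worth making because it is cheap and removes a discretionary, one-sided exclusion from the safety summary.

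**What to change.** - Replace the exclusions in Sections 3.5.2.7 and 5.1.1 with a rule that every such observation is recorded and carries a flag when it is attributed to improvement. The investigator's interpretation is kept as data.
- Tabulate TEAEs with and without flagged events.
- Have the independent Medical Monitor on the Safety Monitoring Committee review the flags.
- Reconcile Sections 3.5.2.7, 5.1.1 and 6.3.2 on D-dimer: whether a rise falls under the rule, who decides, and how that fits its status as a marker under study.

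This alters no treatment rule. It costs one data field, one extra table and slightly higher AE counts. By the date given in Section 1.3 all 15 subjects had received at least 48 weeks of treatment, so past observations would have to be retrieved from diaries and source records. Retrieval of clots will be only as complete as those records, and the report should say so.
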